4.2 Registration Process for DF/HCC and DF/PCC Institutions

The QACT registration staff is accessible on Monday through Friday, from 8:00 AM to 5:00 PM Eastern Standard Time. In emergency situations when a participant must begin treatment during off-hours or holidays, call the QACT registration line at [contact] and follow the instructions for registering participants after hours.

The registration procedures are as follows:

1. Obtain written informed consent from the participant prior to the performance of any study related procedures or assessments.
2. Complete the protocol-specific eligibility checklist using the eligibility assessment documented in the participant's medical/research record. **To be**

eligible for registration to the study, the participant must meet each inclusion and exclusion criteria listed on the eligibility checklist.

Reminder: Confirm eligibility for ancillary studies at the same time as eligibility for the treatment study. Registration to both treatment and ancillary studies will not be completed if eligibility requirements are not met for all studies.

3. Fax the eligibility checklist(s) and all pages of the consent form(s) to the QACT at [contact].
4. The QACT Registrar will (a) validate eligibility, (b) register the participant on the study, and (c) randomize the participant when applicable.
5. The QACT Registrar will send an email confirmation of the registration and/or randomization to the person initiating the registration immediately following the registration and/or randomization.

5. TREATMENT PLAN

5.1 Tumor procurement

At the time of the liver resection at MGH the specimen will be handled according to CVC SOP B1.01 (Appendix) and transferred to DFCI CMCF by an authorized study team member, for example [name] [contact] or [contact]) or [name] [contact]).

5.1.2 Vaccine administration

Treatment will be administered on an outpatient basis. It is expected that patients will have fully recovered from surgery and chemotherapy prior to administration of vaccine, per treating surgeon. In addition, patients may receive postoperative chemotherapy at the discretion of the treatment team. Treatment with GVAX may not start prior to 4 weeks after the last dose of chemotherapy or the operation. GVAX treatment must begin within 6 months of the date of operation. If enough vaccine is made patients may elect to have an additional 6 vaccines if they still meet the eligibility criteria.

Following notification by the treating provider that vaccine may be administered, the CMCF staff will be notified to thaw the vaccine. Vaccines will be retrieved from the CMCF by an authorized study team member as noted, according to CMCF policy and brought to the MGH on ice via the Partners shuttle or in a taxi between 1-4 hours prior to vaccine administration. The vaccine will be stored on ice until it is ready to be administered.

Expected toxicities and potential risks as well as dose modifications for GVAX are described in Section 6 (Expected Toxicities and Dosing Delays/Dose Modification). No

investigational or commercial agents or therapies other than those described below may be administered with the intent to treat the participant's malignancy.

Vaccination Plan					
Agent	Pre-medications; Precautions	Range	Route	Schedule	Cycle Length
GVAX	No premedications	1x10 ⁵ to 1x10 ⁷ cells/vaccine	Subcutaneous and Intradermal	Days 1,8,15, 29,43, 57	57 days

5.1.2.1 Vaccinations will be administered on days 1, 8, 15, and every two weeks thereafter until 6 vaccines have been administered or the patient is removed from study. As indicated in 5.2.2.4, individual vaccine cell dose will vary depending on the final cell yield from vaccine production. The total cell yield will be divided in 6 equal aliquots, and the minimal dose will be 1x10⁵ cells/vaccine and maximal dose will be 1x10⁷ cells/vaccine. This variation in cell dosage is designed to maximize each patient's opportunity of receiving vaccinations and is not based on any expectation of significant differences in toxicity as a function of cell number.

5.1.2.2 All patients receiving at least one vaccination will be evaluable for toxicity. Patients will be considered evaluable for biologic activity if at least six vaccinations have been administered at a given dose level. There is no requirement for a particular number of patients at each cell dose level.

5.1.2.3 Vaccinations may be administered within 24 hours of the scheduled vaccine administration date (e.g. day 8, 15, 29) beginning with the day 8 vaccine.

5.1.2.4 Patients must be greater than 28 days from any chemotherapy, radiotherapy, immunotherapy, systemic glucocorticoid therapy, or resection of hepatic colorectal metastasis.

5.2 Pre-treatment Criteria

5.2.1 Primary Tumor Procurement

5.2.1.1 Patients will undergo a surgical procedure (hepatic resection) to obtain tissue for vaccine preparation.

5.2.1.2 The responsible surgeon will send a portion of the tumor for standard of care pathology review. Then, the surgeon will place the research tumor specimen in sterile media in a sterile container. After gross evaluation by the pathologist of

the entire specimen in the operating room, the tissue will be transferred to the authorized study team member for vaccine processing at the DFCI CMCF.

5.2.1.3 Patients will receive routine post-operative care.

5.2.1.4 At the discretion of the treating physician patients may receive post operative chemotherapy prior to vaccine administration. Participants will undergo a separate standard of care chemotherapy consent session with their treating physician as the chemotherapy is not a part of the investigational agent in this study.

5.2.1.5 If recurrent disease is identified on the restaging scans prior to vaccine, vaccine will not be administered.

5.2.2 Cell Preparation

5.2.2.1 Tumors will be transferred to the CMCF at the Dana-Farber Cancer Institute by approved personnel and processed to single cell suspension by mechanical and enzymatic digestion as required; short-term tumor cultures may be established if necessary to obtain sufficient cells.

5.2.2.2 Tumor cells will be transduced with a replication defective adenoviral vector encoding human GM-CSF.

5.2.2.3 After transduction, the tumor cells will be washed extensively and irradiated with 10,000 cGy.

5.2.2.4 A small aliquot of the transduced cells will be placed into culture and GM-CSF secretion will be determined by ELISA. The target level for GM-CSF production will be at least 40 ng/10⁶ cells/24 hours, although achieving this secretion will not be required for vaccine administration. Routine sterility cultures and testing for endotoxin and mycoplasma contamination will be performed

5.2.2.5 Individual vaccine cell dose will vary depending on the final cell yield from vaccine production. The total cell yield will be divided in 6 equal aliquots, and the minimal dose will be 1x10⁵ cells/vaccine and maximal dose will be 1x10⁷ cells /vaccine. This variation in cell dosage is designed to maximize each patient's opportunity of receiving vaccinations and is not based on any expectation of significant differences in toxicity as a function of cell number.

5.3 Subsequent Vaccines

5.3.1 If in the judgment of the treating physician, the clinical status of the patient following completion of the first six vaccinations permits, the option for expansion of tumor cells previously cryopreserved, vaccine production, and vaccination will be offered to the patient. The patient will need to satisfy the same eligibility criteria as for entry on the first round of treatment, except for the requirement that greater than four weeks have elapsed since prior GVAX immunotherapy. The decision to enter this second phase can be made at any time following completion of the six initial vaccinations required for toxicity evaluation.

It is recognized that initiation of a second round of treatment may obscure the ability to evaluate potential delayed toxicities associated with the first round of vaccination. The likelihood of such toxicities given the experience with earlier melanoma trials seems remote, however, and additional data regarding the safety of repeat courses of vaccine procurement and vaccination is a higher priority. Additional rounds of vaccination may be considered as long as the patient continues to meet eligibility criteria.

5.3.2 For patients proceeding to one additional round of vaccine, the procedures outlined in sections 5.1-5.4 will be followed. It is anticipated that the cell dosage for additional rounds of vaccination may be different from that used in the first round.

5.1.3 Patients may opt to discontinue treatment after the first round of vaccines to undergo another type of treatment or participate in another clinical trial. Patients also have the option of a second round of vaccination if enough vaccine is available. The subject will need to satisfy the same eligibility criteria for entry as done with the first round of vaccines.

5.4 Agent Administration

5.4.1 Vaccinations will be administered on days 1, 8, 15, and every two weeks thereafter until 6 vaccines have been administered or the patient is removed from study. As indicated in 5.2.9, individual vaccine cell dose will vary depending on the final cell yield from vaccine production. The total cell yield will be divided in 6 equal aliquots, and the minimal dose will be 1×10^5 cells/vaccine and maximal dose will be 1×10^7 cells/vaccine. This variation in cell dosage is designed to maximize each patient's opportunity of receiving vaccinations and is not based on any expectation of significant differences in toxicity as a function of cell number.

5.4.2 Vaccinations may be administered within 24 hours of the scheduled vaccine administration date (e.g. day 8, 15, 29) beginning with the day 8 vaccine.

5.4.3 Vaccination Procedure

5.4.3.1 Cells will be thawed in a dedicated laminar flow biosafety cabinet in the CMCF and washed. Cells will be resuspended in a volume of 1 ml. for administration. 2 injections (1/2 dose subcutaneously and 1/2 dose intradermally at the same site with repositioning of the needle) will be given and will constitute a single vaccination. The volume of each injection will be 0.5 ml.

5.4.3.2 Injections will be administered according to standard procedures in the patient's arms, thighs, or trunk on a rotation basis.

5.4.3.3 A treating physician, NP, PA, or RN designated by the PI will administer the injections in the outpatient facilities of the Massachusetts General Hospital.

5.5 Duration of Therapy

Duration of therapy will depend on individual response, evidence of disease progression and tolerance. In the absence of treatment delays due to adverse events, treatment may continue for a total of 6 vaccines or until one of the following criteria applies:

- Disease progression, intercurrent illness that prevents further administration of treatment,
- Unacceptable adverse event(s),
- Participant demonstrates an inability or unwillingness to comply with the protocol requirements.
- Participant decides to withdraw from the study, or
- General or specific changes in the participant's condition render the participant unacceptable for further treatment in the opinion of the treating investigator.

If enough vaccine is available and patients meet eligibility criteria he/she may be a candidate for an additional 6 vaccines.

5.6 Duration of Follow Up

Participants will be followed for 3 months after the last vaccine then every 6 months for 3 years, then yearly for up to 5 years. Since they are receiving a gene modified product, each patient will remain in long term follow up and followed annually for survival for a period of fifteen years for surveillance and toxicity evaluation.

6. EXPECTED TOXICITIES AND DOSING DELAYS/DOSE MODIFICATIONS

6.1 Anticipated Toxicities

6.1.1 GM-CSF is widely used for accelerating hematopoietic recovery and its spectrum of toxicity well established. It is likely that the highest dose level used in this study will generate far lower amounts of GM-CSF than the usual starting dose for systemic application (350 µg/day). While we cannot predict the exact toxicities attributable to local secretion of GM-CSF delivered by adenoviral mediated gene transfer, toxicities observed from the previous trial were restricted to erythema, pruritus, and swelling. Local toxicities of GM-CSF protein injection have included pustular eruption, necrotizing vasculitis, erythema, pruritus, recall erythema at previous injection sites, general papular rash, and phlebitis. Systemic toxicities have included fever, bone pain, malaise and diarrhea, transient liver function test (LFT) abnormalities, leukopenia, leukocytosis, arthralgia, dyspnea, fluid retention, serous effusions, and recrudescence of various autoimmune diseases.

6.1.2 A theoretical potential exists for the induction of auto-immune disease by the vaccination, although no evidence of vitiligo or visual disturbances was noted in the previous melanoma studies. Mechanisms which allow the immune system to recognize tumor antigens in principle could also lead to the breakdown of tolerance to normal self antigens. Because of this concern, patients entered on study will be closely monitored for any clinical or laboratory evidence of auto-immune phenomena.

6.1.3 A final source of toxicity in this study relates to the use of adenoviral vectors. Wild type adenovirus serotype 5 (from which the vector used in this study is derived) is associated with an upper respiratory infection and conjunctivitis. There is controversy regarding a role in infantile intussusceptions. Other adenovirus serotypes are associated with cystitis, gastroenteritis, and pneumonia in military recruits during basic training. The adenoviral vector used in this study will be certified to contain less than one replication competent serotype 5 viral particle per vaccine inoculum. In the event that recombination between a latent wild type adenovirus and the introduced adenoviral vector occurs in the tumor cell, this will not lead to production of a replication competent GM-CSF expressing virus, as the GM-CSF cDNA is inserted in the E1 deleted region of the vector. Transduced cells will be injected into the skin; thus in the absence of an open wound, there is no significant risk of transmitting the virus to close contacts. If skin breakdown does occur, the skin should be covered with an adherent bandage until healing has occurred.

6.1.4 Lethal irradiation represents an important safeguard against some toxicities associated with vaccinating cells. Irradiation will prevent the outgrowth of tumor cells potentially rendered more virulent by virtue of in vitro manipulation or insertional mutagenesis, as well as the autonomous proliferation of any non-neoplastic elements in the vaccinating inoculum induced by the autocrine secretion of GM-CSF. Toxicities observed from the previous adenovirus-based melanoma trial were restricted to erythema, pruritus, and swelling (all easily treated with either ice packs or topical lotions such as Aloe cream). It is possible,

although unlikely, that additional toxicities including blister formation or ulceration may occur.

6.2 Toxicity Management

6.2.1 Treatment of toxicities will be supportive. If possible, symptoms should be managed symptomatically. In the case of toxicity, appropriate medical treatment should be used. This may include for example, cold compresses and or moisturizing lotions applied to localized vaccine site reactions.

All adverse events experienced by participants will be collected from the time of the first vaccine administration, through the study and until the final study visit. Participants continuing to experience toxicity at the off study visit will be followed until the toxicity has resolved, stabilized, determined to be irreversible or the participant is lost to follow-up.

6.2.2 General Concomitant Medication and Supportive Care Guidelines

Patients are prohibited from taking steroids, NSAIDS, antihistamines (by mouth or IV) but may use local measures such as ice packs or topical moisturizers between the time of the first vaccination and two weeks after the sixth vaccination. Use of topical anesthetics such as EMLA © and topical antihistamines are prohibited at injection sites.

6.3 Dose Modifications/Delays

6.3.1 There will be no dose adjustments for Grade 1 and 2 toxicities seen on this study.

6.3.2 If a patient develops grade 3 toxicity attributable to the vaccine, additional treatment will be withheld until all toxicity has resolved, then he or she may be retreated at monthly intervals. If the toxicity recurs with resumption of vaccine then the patient will be removed from study. If a patient develops a grade 4 toxicity attributable to the vaccine, he or she will be removed from study. If three grade 4 or greater toxicities attributable to the vaccine are observed at any time, the trial will be suspended to investigate the causes of these unexpected toxicities.

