11.3 Reporting Requirements

All life-threatening events which may be due to vaccine administration

All fatal events while on study

All such events will be reported to the DFCI Office for the Protection of Research Subjects by the protocol chairperson within 48 hours.

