11.4 Reporting to the Principal Investigator

11.4.1 Serious Adverse Event Reporting

All serious adverse events that occur after the initial dose of study treatment, during treatment, or within 30 days of the last dose of treatment must be reported to the DF/HCC Overall Principal Investigator on the local institutional SAE form. This includes events meeting the criteria outlined in Section 9.1, as well as the following:

- Grade 2 (moderate) and Grade 3 (severe) Events – Only events that are unexpected and possibly, probably or definitely related/associated with the intervention.
- All Grade 4 (life-threatening or disabling) Events – Unless expected AND specifically listed in the protocol as not requiring reporting.
- All Grade 5 (fatal) Events – When the participant is enrolled and actively participating in the trial OR when the event occurs within 30 days of the last study intervention.

Note: If the participant is in long term follow up, report the death at the time of continuing review.

Participating investigators must report each serious adverse event to the DF/HCC Overall Principal Investigator within 24 hours of learning of the occurrence. In the event that the participating investigator does not become aware of the serious adverse event immediately (e.g., participant sought treatment elsewhere), the participating investigator is to report the event within 24 hours after learning of it and document the time of his or her first awareness of the adverse event. Report serious adverse events by telephone, email or facsimile to:

[name].
[contact]
[contact]
[contact]

Within the following 24-48 hours, the participating investigator must provide follow-up information on the serious adverse event. Follow-up information should describe whether the event has resolved or continues, if and how the event was treated, and whether the participant will continue or discontinue study participation.

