11.5 Reporting to the IND Sponsor

Adverse events meeting the following criteria, regardless of relatedness or expectedness, must be reported to the IND Sponsor (or designee) for those subjects who received at least 1 vaccine:

- Grade ≥ 3 Non-Hematologic
- Grade ≥ 3 Hematologic
- All Grade 5 events

Reporting to the Sponsor begins at time of first vaccine and goes until 15 years after the subject's last vaccine.

All events meeting the criteria above must be forwarded to the IND Sponsor (or designee) within 2 business days of knowledge of the event using an FDA Form 3500A.

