11.7 Reporting to the Food and Drug Administration (FDA)

[name] as holder of the IND (IND Sponsor), will be responsible for all communication with the FDA. The IND Sponsor will report to the FDA, regardless of the site of occurrence, any adverse event that is serious, unexpected and reasonably related (i.e., possible, probable, definite) to the study treatment.

Unexpected fatal or life-threatening experiences associated with the use of the study treatment will be reported to FDA as soon as possible but in no event later than 7 calendar days after initial receipt of the information.

All other serious unexpected experiences associated with the use of the study treatment will be reported to FDA as soon as possible but in no event later than 15 calendar days after initial receipt of the information.

Events will be reported to the FDA by telephone ([name]) or by fax ([name]) using Form FDA 3500A (Mandatory Reporting Form for investigational agents) or FDA Form 3500 (Voluntary Reporting Form for commercial agents). Forms are available at <http://www.fda.gov/medwatch/getforms.htm>.

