12.2 Safety Meetings

The DF/HCC Data and Safety Monitoring Committee (DSMC) will review and monitor toxicity and accrual data from this trial. The committee is composed of clinical specialists with experience in oncology and who have no direct relationship with the study. Information that raises any questions about participant safety will be addressed with the Principal Investigator and study team.

The DSMC will meet quarterly and/or more often if required to review toxicity and accrual data. Information to be provided to the committee may include: up-to-date participant accrual; current dose level information; DLT information; all grade 2 or higher unexpected adverse events that have been reported; summary of all deaths occurring within 30 days for Phase I or II protocols; for gene transfer protocols, summary of all deaths while being treated and during active follow-up; any response information; audit results, and a summary provided by the study team. Other information (e.g. scans, laboratory values) will be provided upon request.

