14 STATISTICAL CONSIDERATIONS

The study consists of a single stage of accrual of patients with hepatic metastases from colorectal cancer.

Patient safety will be assured by monitoring the number of patients who fail to receive the first six scheduled vaccinations because of toxicity. If three or more patients experience grade 4 or worse toxicity due to the vaccine before completing six immunizations, the study will be terminated. If the unknown true rate of grade 4 or worse toxicity is 0.05, then the probability of early termination is 0.04. Similarly, if the unknown true rate is 0.25, then the probability of early termination is 0.76.

Feasibility will be assessed by the ability to make vaccine from resected hepatic metastases in quantities sufficient for six vaccinations. Fifteen patients will be entered. If fewer than 9 patients receive six vaccinations, the study will cease. A success rate under 65% (true rate) may imply that the method needs further development or that the amount of tissue available in this population limits the feasibility of this strategy. This study will have 75% power against the null of 45% success rate, testing at the one-sided 0.18 significance level and using exact methods.

The percentage of patients who successfully receive 6 vaccinations and the number of vaccinations received by patients will be described. Any late occurrences of grade 3 or worse toxicity and the vaccination number at which they occur will be reported.

For the correlative science it is unclear which changes will occur in the circulating immune cells since a study like this has never been done in patients with resected hepatic metastases from colorectal cancer. Currently we do not have estimates to present a statistical model or plan. No changes in the correlative science should influence administration of the vaccine in the patients.

Table 1. 90% confidence intervals for the true proportion of patients who receive all six injections

Observed number of	Observed rate of patients	90% confidence interval for
--------------------	---------------------------	-----------------------------

patients who receive all six injections	who receive all six injections	the true rate of patients who receive all six injections
8	53%	(30%, 76%)
10	67%	(42%, 86%)
11	73%	(49%, 90%)
12	80%	(56%, 94%)

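### Neither trial-level toxicity rule separates a vaccine-attributed death from a non-fatal grade 4 event, so a first or second such death triggers reports but no required pause in dosing or enrolment

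*Combined protocol and SAP*

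**What the plan says.** The protocol has two trial-level toxicity rules. Section 6.3.2: "If three grade 4 or greater toxicities attributable to the vaccine are observed at any time, the trial will be suspended". Section 14: "If three or more patients experience grade 4 or worse toxicity due to the vaccine before completing six immunizations, the study will be terminated". Section 11.1 identifies grade 5 as fatal, so under either rule a death is a qualifying event with the same weight as a non-fatal grade 4 event. The other toxicity actions in 6.3.2 (withholding vaccine after grade 3, removal from study after grade 4) concern only the affected patient.

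For a vaccine-attributed death the text requires the following:

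- Overall principal investigator, 11.4.1, for events up to 30 days after the last dose: "Participating investigators must report each serious adverse event to the DF/HCC Overall Principal Investigator within 24 hours of learning of the occurrence".
- DFCI office, 11.3, for fatal events on study: "All such events will be reported to the DFCI Office for the Protection of Research Subjects by the protocol chairperson within 48 hours".
- IND sponsor, 11.5: grade 5 events "must be forwarded to the IND Sponsor (or designee) within 2 business days of knowledge of the event".
- FDA, OBA and the biosafety committee, 11.7 to 11.9: within 7 calendar days if the death is unexpected and "reasonably related (i.e., possible, probable, definite) to the study treatment" (or, for OBA and the biosafety committee, to the gene transfer product).
- Data and Safety Monitoring Committee (DSMC), 12.2: "The DSMC will meet quarterly and/or more often if required to review toxicity and accrual data". What it may be given includes, "for gene transfer protocols, summary of all deaths while being treated and during active follow-up". Information that raises safety questions is to be addressed with the principal investigator and study team.

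**The concern.** These are duties to report, review and discuss. None makes a death stop vaccine for other patients, stop enrolment, or call an unscheduled DSMC meeting. The only trial-wide actions on toxicity wait for a third grade 4 or worse event.

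At stake is the exposure of other patients between a first or second vaccine-attributed death and the review of its cause. The patients have been completely resected, the product is gene-modified, and safety is the primary objective (1.2). Section 6.1.4 reports nothing beyond erythema, pruritus and swelling in the earlier adenovirus-based melanoma trial, so one attributed death would already lie far outside the expected profile. Section 6.3.2 gives investigation of unexpected toxicities as the purpose of suspension; a single attributed death meets that purpose.

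**Working it through.** **1. The plan's own figures.** Inputs: 15 patients and termination at three or more (Section 14). With X binomial(15, p), P(X ≥ 3) = 1 − P(0) − P(1) − P(2).

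- p = 0.05: 1 − 0.4633 − 0.3658 − 0.1348 = 0.036 (stated 0.04).
- p = 0.25: 0.764 (stated 0.76).

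Both reproduce. They describe the pooled rule and say nothing about deaths as such.

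**2. Chance that the gap is reached.** The documents give no vaccine-death rate, so d is an assumption. P(at least one death among n vaccinated) = 1 − (1 − d)^n. The number vaccinated is also uncertain: 14.3.1 accepts 60% of enrolled patients starting vaccine, and 0.60 × 15 = 9.

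- d = 1%, n = 9: 1 − 0.99^9 = 0.087, about 9%.
- d = 1%, n = 15: 1 − 0.99^15 = 0.140, about 14%.

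The chance that a death occurs while the pooled count stays below three also depends on the non-fatal grade 4 rate. For n = 15, counting one event per patient:

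| Fatal rate | Non-fatal grade 4 rate | P(at least one death, count below three) |
|---|---|---|
| 1% | 0% | 0.14 |
| 1% | 4% | 0.12 |
| 5% | 0% | 0.50 |
| 5% | 5% | 0.37 |
| 10% | 15% | 0.13 |

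These are chances of the situation arising. They do not measure harm from the missing pause.

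**3. Exposure of others if nobody acts before a quarterly meeting.** Inputs: six doses on days 1 to 57, a 56-day course (5.1.2); enrolment over two years, 730 days (14.2); quarterly meetings, taken as 91 days apart (12.2), so a mean wait of 45.5 days. Assumptions: even starts, one round of vaccine, and a death at a random time while accrual continues. With m other vaccinated patients and wait w:

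- patients dosed ≈ (m/730) × (56 + w)
- doses ≈ (m/730) × 6 × w

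Results:

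- 15 vaccinated (m = 14), w = 45.5: 14/730 × 101.5 = 1.95 patients; 14/730 × 6 × 45.5 = 5.2 doses. A simulation with the wait varying evenly from 0 to 91 days gives 1.88 patients and 5.2 doses.
- 9 vaccinated (m = 8), w = 45.5: 8/730 × 101.5 = 1.1 patients; 8/730 × 6 × 45.5 = 3.0 doses.
- Longest wait, 15 vaccinated, w = 91: 14/730 × 147 = 2.8 patients; 10.5 doses.
- Starts spread over 1 or 3 years, 15 vaccinated, varying wait: 3.75 or 1.26 patients in the same simulation.

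**4. Patients whom a pause would delay (m = 14).** In mid-course: 14/730 × 56 = 1.07. Due to start during a 45.5-day pause: 14/730 × 45.5 = 0.87.

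**The case against.** The strongest reply is that the protocol is not passive after a death. The principal investigator hears within 24 hours and the DFCI office within 48. Safety questions must be addressed with the investigator (12.2), the DSMC can meet sooner than quarterly, and 13.3 permits departure from the protocol to remove an immediate hazard. Section 13.3 also adopts federal regulations and institutional policies, and 11.1 adopts institutional guidelines for gene transfer studies; none is reproduced here, and any might require a hold. All of this stands. It makes early intervention likely, and it makes the exposure figures conditional on every recipient of those reports doing nothing. It does not put a required pause into the protocol.

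A second reply is that one death need not count as one event. Section 6.3.2 counts toxicities, so a death with two other attributed grade 4 toxicities in the same patient could suspend the trial. That is right for 6.3.2. Section 14 counts patients, and a death without such accompanying events counts once under either rule.

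A third is that large probabilities come from extreme inputs. This also stands: the 50% figure needs a 5% vaccine-death rate and no non-fatal grade 4 events, which fits poorly with the mild toxicity reported earlier. The 1% figures are the more sensible illustration, and even they are assumptions.

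**Conclusion.** The point holds as a gap in the written rules. Neither rule distinguishes a vaccine-attributed death from a non-fatal grade 4 event, and nothing in the documents obliges anyone to pause dosing or enrolment after the first or second such death.

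A reader might go further and infer that dosing would in practice continue through two deaths, or that the protocol forbids stopping earlier. The documents support neither: reporting is fast, 12.2 requires safety questions to be addressed, and 13.3 allows immediate action. Nor is there an arithmetic error, since 0.04 and 0.76 are right for the rule as written.

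The size is modest and illustrative: about a 9% to 14% chance of any vaccine death at an assumed 1% rate, with 9 to 15 vaccinated. In the scenario where no one acts before a quarterly meeting, about 1.1 to 1.9 other patients receive about 3 to 5 doses at the mean wait, given even starts over two years. This is a cheap improvement, not a flaw that undermines the trial.

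**What to change.** Add to 6.3.2 and Section 14:

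> After any grade 5 event possibly, probably or definitely related to the vaccine, occurring from first vaccination to 30 days after the last (or later if judged probably or definitely related), no further vaccine is given and enrolment pauses. An ad hoc DSMC review is requested promptly, without waiting for the quarterly meeting, and dosing resumes only on its written recommendation. Patients in mid-course may then resume outside the 24-hour window, delayed doses count toward six, the pause is not counted in the 6-month start limit, and patients waiting to start repeat baseline evaluation if it is more than 4 weeks old.

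Deaths still count toward the three-event rules. If trigger probabilities are printed beside 0.04 and 0.76, label them as lower bounds covering true vaccine deaths only (0.14 at a 1% rate with 15 vaccinated), because a death judged possibly related would also trigger the pause. The other differences between the two rules (suspend or terminate, toxicities or patients, any time or before six doses) need separate attention.

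The cost is a short paragraph in two places and a reversible pause. With 15 vaccinated, the pause delays about 1 patient in mid-course plus up to about 0.9 due to start over 45 days, fewer if review is prompt. Vaccine is cryopreserved (7.3), so delay need not lose product. Some pauses would follow misattributed deaths, at a rate the documents do not allow to be estimated.
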